DESIGN: A nationwide stepped wedge cluster randomised trial in which primary care midwifery practices will be randomised.

PARTICIPANTS: 15,000 women who receive/continue care in the participating midwifery practice after the 20 week structural ultrasound and who have a singleton pregnancy.

INTERVENTION AND CONTROL STRATEGIES: In all midwifery practices, growth will be monitored using standardised symphysis fundal height (SFH) measurement. In the intervention strategy two routine US examinations will be performed (between 28-30 weeks and 34-36 weeks), while in the control strategy US examination will only be performed when clinically indicated. In both groups the IRIS consensus-based protocol will be followed if intrauterine growth retardation is suspected.

PRIMARY OUTCOMES: The clinical primary outcome is a dichotomous composite measure 'severe adverse perinatal outcome' up to 7 days after birth, including: perinatal death; Apgar score below 4 at 5 minutes after birth; impaired consciousness; need for assisted ventilation for more than 24 hours; asphyxia; septicaemia; meningitis; bronchopulmonary dysplasia; intraventricular haemorrhage; cystic periventricular leukomalacia; neonatal seizures or necrotizing enterocolitis. Also direct and indirect costs are primary outcomes.

SAMPLE SIZE: A total of 15,000 women in 60 midwifery practices; 7,500 women per strategy.

MAIN DATA ANALYSIS AND ECONOMIC EVALUATION: Multivariable logistic regression analyses, taking into account the clustered design. The economic evaluation will consist of a cost-effectiveness and a cost-utility analysis and will be performed from both a health care provider and societal perspective. We will base all primary analyses on intention to treat.

DURATION: 48 months.

Problem definition

DETECTION OF SMALL-FOR-GESTATIONAL-AGE

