The IRIS study is designed as a stepped wedge cluster randomised trial (c-RCT, Figure 1). A stepped wedge design is a type of crossover design in which different clusters cross over (switch treatments) at different time points. Clusters cross over in one direction only; typically from control to intervention. The time at which a cluster starts with the intervention is randomized; more than one cluster may start the intervention at a particular time point [Hussey 2007]. The advantages of a stepped wedge design are: a) all practices will offer the intervention for a shorter or longer period of time, which may encourage them to take part, b) practices will serve as their own control for a variable time period which will reduce the variation in characteristics and practice management between the intervention and control strategy group. Note: in contrast to many other stepped wedge c-RCTs the women participating in our study will receive the intervention strategy OR control strategy.

Midwifery practice will be the unit of randomisation. Randomisation per practice rather than per midwife or client has the advantage of minimising contamination and therefore maximising contrast between the intervention and control strategy group.

All midwifery practices (n=60) will start in the control strategy and provide obstetric care as usual. At intervals of 3 months, 33,3% of all practices (n=20) will change status from control to intervention group and will start offering the intervention, i.e. routine biometry ultrasound in the third trimester of pregnancy. To balance the number of women in the intervention and control group, practices will be stratified prior to randomisation in large and small practices, with the average practice size as the cut-

off point (i.e. 250 clients a year). Within these two strata, a computer-generated random sequence will determine the order in which practices move from control to intervention status. This randomisation will take place after practices have been recruited for participation in the study and before data collection begins.

Figure 1: The IRIS stepped wedge design | UC = control strategy; INT= intervention strategy; US= ultrasonography

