Given the above mentioned ICCs for neonatal mortality, the formula to correct for clustering $[1 + (n-1) * ICC]$ with $n = 250$ (i.e. average cluster size) gives a required sample size for the IRIS study of 14,547 (ICC 0.0003) to 20,304 (ICC 0.002). For two reasons we expect the ICC in the IRIS study to be much more similar to 0.0003 than to 0.002. Our first argument is that the ICCs reported in the paper of Pagel et al. (2011) are based on prevalence rates ranging from 1.5% to 5.9% which is higher than the expected severe perinatal outcome in the IRIS study. As ICCs are associated with the prevalence of the outcome of interest [Pagel et al., 2011] we may expect the ICC in the IRIS study to be even lower than 0.0003. Our second argument is that midwife practices will offer both the control strategy (i.e. US on indication) and, later on, the intervention strategy (i.e. routine US). This will reduce the variation in characteristics and practice management between the intervention and control strategy group and thereby lower the size of the ICC .

Taking into account an ICC of 0.0003, the required sample size is 14,547 women. As not all women who will sign the informed consent form may receive care in the participating midwifery practice at the start of the third trimester, we adjusted this figure to a total of 15,000.

Effectiveness analyses

Firstly, we will assess the similarity between baseline characteristics of women having had the intervention strategy and women having had the control strategy. Secondly, we will compare baseline characteristics of drop-outs and completers by using logistic regression analysis. Thirdly, we will use multivariable logistic multilevel analyses to investigate the effect of routine US screening on perinatal outcome, adjusting for possible clustering of observations and confounders (e.g. ethnicity, maternal age, weight and height, smoking, alcohol use, drug use, blood pressure). We will base our analyses on intention to treat and set the level of significance at $p < 0.05$.

We will perform a subgroup analysis for women without US indication and for nulliparous women.

In addition to the intention to treat analysis we will also perform a per-protocol analysis, restricted to the women in the intervention group who received the two US examinations and to the women in the control group who did not receive any screening US.

Cost-effectiveness and cost-utility analyses

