Both cost-effectiveness and cost-utility analyses will be done according to the intention-to-treat principle. ICERs and the ICUR will be calculated by dividing the difference in mean costs between the two groups by the difference between the two groups in effects and in QALYs, respectively. Bias-corrected and accelerated bootstrapping with 5000 replications will be used to estimate 95% confidence intervals around cost differences and the uncertainty surrounding the ICERs and ICUR. Uncertainty surrounding the ICERs and ICUR will be graphically presented on cost-effectiveness planes. Cost-effectiveness acceptability curves will also be estimated using the net benefit framework.[Stinnett & Mullahy, 1998] Cost-effectiveness acceptability curves show the probability that routine third trimester ultrasound screening to detect IUGR is cost-effective in comparison with usual care for a range of different ceiling ratios thereby showing decision uncertainty.

We will perform a subgroup analysis for women without US indication and for nulliparous women.

We will explore the robustness of the results of our intention to treat analysis by a per-protocol sensitivity analysis. Furthermore, we will repeat the pregnancy related cost-effectiveness analysis from a health care provider perspective and the cost-effectiveness analysis from a societal perspective using solely the data of the 600 randomly selected women participating in the survey study.

REFERENCES

Alfirevic Z, Stampalija T, Gyte GM. Fetal and umbilical Doppler ultrasound in high-risk pregnancies. *Cochrane Database Syst Rev* 2010a;(1):CD007529.

Alfirevic Z, Stampalija T, Gyte GM. Fetal and umbilical Doppler ultrasound in normal pregnancy. *Cochrane Database Syst Rev* 2010b;(8):CD001450.

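### The cost contrasts, a primary outcome, are specified as differences in group means with no term for calendar period or practice, although the stepped wedge ties strategy to calendar time

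*Protocol*

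**What the plan says.** The protocol summary states: "Also direct and indirect costs are primary outcomes". Under the heading Cost-effectiveness and cost-utility analyses, "ICERs and the ICUR will be calculated by dividing the difference in mean costs between the two groups" by the between-group difference in effects (ICERs) or in QALYs (ICUR). On uncertainty, "Bias-corrected and accelerated bootstrapping with 5000 replications will be used to estimate 95% confidence intervals around cost differences" and around the ratios. That section also covers cost extrapolation, multiple imputation, intention to treat, cost-effectiveness planes, acceptability curves and sensitivity analyses. It names no practice effect, covariate, calendar period or resampling unit.

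The clinical analysis is treated differently. Under Effectiveness analyses the logistic model is multilevel, "adjusting for possible clustering of observations and confounders". The summary puts the clustering clause in the logistic sentence, "Multivariable logistic regression analyses, taking into account the clustered design", and does not repeat it in the economic sentence that follows. Neither place names calendar period.

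On design: "The IRIS study is designed as a stepped wedge cluster randomised trial". All 60 practices start under control. "At intervals of 3 months, 33,3% of all practices (n=20) will change status from control to intervention group". Women are recruited during months 1 to 12.

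**The concern.** In a stepped wedge, strategy is tied to calendar time: early women are mostly controls and late women mostly intervention. A difference in group means therefore mixes the effect of the strategy with any change over time in how much care is used. This is a bias, and a wider interval does not remove it.

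The protocol's background gives reason to expect such change. It reports that routine third-trimester scanning is spreading in the Netherlands, that growth in scanning has raised health care costs, and that a budget cut was announced in response. These could push resource use in opposite directions, so the sign of the bias cannot be told in advance.

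Women within a practice may also resemble each other in care use. A bootstrap that resamples women individually would miss this. At stake is the second objective, cost-effectiveness, with its intervals, planes and acceptability curves.

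**Working it through.** **The plan's own figure.** The protocol gives no sample size or power for costs. Its clinical figure reproduces: 13,536 × (1 + 249 × 0.0003) = 14,547. The ICC of 0.0003 refers to the clinical outcome and says nothing about costs.

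**Inputs from the protocol.** 60 practices; 20 switching at each 3-month step; 12 months of recruitment; 15,000 women, 7,500 per strategy; 600 random survey women in the cost-utility analysis.

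**Assumptions.** Switches fall after months 3, 6 and 9 (Figure 1 is not shown). Practice-quarters are of equal size, and the survey women are spread over them in the same way. The practice effect is constant over time unless stated. Cost ICCs are 0.01 to 0.05, because the protocol gives none. Total cost variance is set to 1.

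**Layout** (0 = control, 1 = intervention; quarters 0 to 3):
- first 20 practices: 0 1 1 1
- second 20: 0 0 1 1
- third 20: 0 0 0 1

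This gives 6 control and 6 intervention group-quarters, in line with 7,500 women each. Quarter 0 is all control and quarter 3 all intervention.

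**Time gap.** Mean control quarter = (0 + 0 + 1 + 0 + 1 + 2)/6 = 0.67. Mean intervention quarter = (1 + 2 + 3 + 2 + 3 + 3)/6 = 2.33. The gap is 1.67 quarters = 5 months. A linear drift of X per quarter, common to all practices, therefore adds 1.67X to the crude difference.

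For scale, assume a drift of 0.01 SD per month, so a bias of 5 × 0.01 = 0.05 SD. The naive standard error is √(4/N): 0.0163 SD at N = 15,000 and 0.0816 SD at N = 600. With no true effect and no clustering, a two-sided 5% test would reject in about 86% and 9% of trials respectively.

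**Clustering of the crude difference.** Each practice-quarter has weight +1/120 or −1/120. The weights sum to +2/120 in each practice of the first group, 0 in the second and −2/120 in the third. The practice-effect multiplier is 40 × (2/120)² = 40/3600 = 0.0111. Relative to resampling women, the true variance is

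(1 − ICC) + ICC × 0.0111/(4/N).

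- N = 15,000, ICC 0.01: 0.99 + 0.01 × 41.67 = 1.41; SE ratio 1.19; coverage of a nominal 95% interval 90.2%.
- N = 15,000, ICC 0.05: 0.95 + 0.05 × 41.67 = 3.03; SE ratio 1.74; coverage 74.0%.
- N = 600, ICC 0.01: 0.99 + 0.01 × 1.67 = 1.01; coverage 94.9%.
- N = 600, ICC 0.05: 0.95 + 0.05 × 1.67 = 1.03; coverage 94.6%.

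The N = 15,000 lines treat costs as observed for every woman.

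**Precision cost of adjusting for period.** The share of practices on intervention by quarter is 0, 1/3, 2/3, 1. The mean of p(1 − p) is (0 + 2/9 + 2/9 + 0)/4 = 1/9, against 1/4 without period terms. The variance ratio is 0.25/(1/9) = 2.25 and the SE ratio 1.50 at ICC 0. A generalised least squares calculation with fixed periods and a random practice effect gives SE ratios of 1.52 to 1.57 (N = 600) and 1.75 to 1.81 (N = 15,000) for ICC 0.01 to 0.05. If the within-practice correlation between quarters is only 0.8 of that within a quarter, the N = 15,000 figures become 1.82 to 2.29.

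**The case against.** The strongest reply is that the text defines a ratio and does not prescribe a crude estimator. Any ICER is a difference in mean costs over a difference in effects, and model-adjusted means would satisfy that wording. The protocol never says unadjusted, and a bootstrap of whole practices is compatible with what it states. An analysis plan that is not shown may settle both. So one cannot assert that women will be resampled, and the clustering figures stay conditional. What the reply does not meet is that the protocol sets out the economic estimator in some detail for a primary outcome, and reserves adjustment for the clinical model. Followed as written, the contrast is confounded with time.

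Three stronger readings are tempting but not supported:
- A reader might infer that price inflation enters the cost difference directly. Under the heading on costs as a primary outcome, care is valued at standard published unit costs, so the drift that matters is in volumes: scans, referrals, admissions.
- A reader might take the 1.5-fold SE ratio as proof that the planned intervals are too narrow. It compares two estimators and is the price of period adjustment. With no clustering and no trend, the crude interval covers correctly.
- A reader might object to the repeat of the cost-effectiveness analyses "using solely the data of the 600 randomly selected women participating in the survey study", because so few events would occur there. It is a labelled robustness check, and its imprecision would show in the bootstrap. Changing it is a matter of preference.

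The 15,000-women clustering figures are also only indicative, because detailed costs come from 600 random and 400 selected women and are extrapolated to the rest.

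**Conclusion.** The point holds, chiefly for calendar time. As written, all three economic analyses rest on a contrast in which intervention women are recruited 5 months later on average. The resulting bias is 1.67 times any quarterly drift in resource use. The documents make such drift plausible but give no size or sign for it. The 5 months depends on the assumed switch dates.

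Clustering is the lesser part and depends on what is resampled. It matters for the two 15,000-women cost-effectiveness analyses if women are the unit, and is negligible for the 600-women cost-utility analysis. It would be wrong to say that every economic interval is too narrow. The omission of calendar period is not confined to the economic section, since the clinical model names none either.

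**What to change.** Estimate the cost, effect and QALY differences from regression models with fixed calendar-period terms and a practice effect, and form the ICERs and ICUR from those estimates. Add the same period terms to the clinical model under Effectiveness analyses, so that both primary outcomes rest on the same adjustment.

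State that the bootstrap resamples whole practices within switch sequence and practice-size stratum. In each replicate, refit the models and repeat the imputation and the cost extrapolation, so that planes and acceptability curves carry the full uncertainty.

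No change to recruitment or data collection is needed. The cost is more programming and computing, because the resampling has to enclose the extrapolation and imputation steps. Precision also falls: the period-adjusted standard error is about 1.5 to 1.8 times the naive one with a practice effect constant over time, and larger in the 15,000-women analyses if it is not. The change should be fixed before the data are analysed.
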